1.2.5 Safety Endpoint

Adverse events, vital signs, clinical laboratory tests and ECG test results.

1.3 Hypothesis to be Tested

The primary endpoint of CSF biomarker will be analyzed by ANCOVA at a significant level of 5% to test the null hypothesis:

H₀:µi = µj H₁:µi ≠ µj

For all $i \neq j$, where μ_i indicates the mean observation for a particular CSF biomarker endpoint for the ith treatment.

Type text h

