1.2 Study Endpoints

1.2.1 Primary Endpoint

The primary endpoint for this study will be to evaluate the change in value of specific cerebral spinal fluid (CSF) biomarkers from the second screening to Day 28 between each dose group and placebo.

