1.2.2 Secondary Endpoint

- The secondary endpoint for this study will be to evaluate the change in CSF biomarkers from the second screening to Day 28 within the study treatment groups.
- The secondary endpoint for this study will be to evaluate the change in Cambridge Cognition testing from the Day 1 to Day 28 between each dose group and placebo
- ٩
- The secondary endpoint for this study will be the dose-response of the study drug.

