2.0 Background

2.1 Study Design

This Phase 2b study is a randomized, double-blind, placebo-controlled trial of PTI-125 oral tablets given to patients with mild to moderate Alzheimer's Disease. Sixty patients are expected to be enrolled in the trial and randomized to one of the three cohorts. Cohorts will receive placebo or PTI-125 at 50 or 100 mg twice a day.

Two screening visits will be scheduled within 30 days of start of the study (Figure 1) Subjects meeting the initial screening criteria will return for a cerebrospinal fluid (CSF) draw at a second screening visit. A second CSF sample will be collected at day 28 visit for CSF biomarkers as well as analysis of PTI-125. Cambridge Cognition testing will be conducted at the second Screening visit, Day 1 and at the Day 28 visit.

On Screening visit 1 and Day 28, patients will be assessed for suicidality via the C-SSRS.

Subjects will report to the clinic on the morning of Day 1 and the following will be conducted: Cambridge Cognition testing, a full physical exam, an ECG and a blood draw for clinical labs and biomarkers. Subjects will be monitored for Adverse Events (AE) and Vital Signs (VS) will be taken through 2 hours post- dosing. Subjects will return to the clinic on Days 7, 14 and 28 for blood draws for clinical laboratory testing, safety assessments of vital signs, ECGs.

PK blood samples will be obtained prior to the first dose on Day 7, Day 14, and Day 28 for C_{min} values. On Day 28, there will be a CSF draw after the last dose, and an additional PK blood sample will be obtained after this CSF draw for calculation of CSF/plasma ratio.

Blood samples for testing in PTI-125Dx, the companion diagnostic/biomarker, mTOR activation and other potential blood-based biomarkers will be drawn on Day 1 and Day 28. The Day 14 blood sample will also be used for APOE genotyping. A CSF sample collection will be performed on Day 28 for neurogranin, neurofilament light chain, total tau, pTau (T181), A β 42, A β 40, YKL40, IL-6, IL-1 β , TNF α and other potential CSF biomarker assays as well as bioanalysis of PTI-125.

Figure 1. Study Design Schema

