4.4 Planned Analyses

4.4.1 Statistical Summaries: Descriptive and Inferential

All statistical tests will be two-sided and a difference resulting in a p-value of less than or equal to 0.05 will be considered statistically significant.

All p-values will be rounded to and displayed in four decimals. If a p-value less than 0.0001 occurs, it will be shown in tables as <0.0001.

Descriptive summaries of variables will be provided where appropriate. For continuous variables, the number of nonmissing values (n) and the median, mean, standard deviation, minimum, and maximum will be tabulated by treatment. For categorical variables, the counts and proportions of each value will be tabulated by treatment.

Data will be presented as listings where applicable. Data not subject to analysis according to this plan will not appear in any tables or graphs but will be included in the data listings.

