6.1 Efficacy Endpoints

The efficacy endpoints are summarized in Table 2.

Table 2. Summary of Efficacy Parameters

Parameter	Method of Determination / Derivation
Primary Efficacy Endpoint	
Change from Screening Visit 2 of the specific CSF biomarker on Day 28	Change = Day 28 – Screening Visit 2
The Cambridge Cognition tests results	NA

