6.2 Efficacy Analyses

6.2.1 Primary Efficacy Analysis

CSF Biomarkers

The baseline, post baseline, and change from baseline values will be summarized by treatment group based on the FAS population. The change from baseline on Day 28 will be analyzed by using a General Linear Model for the ANCOVA. The model will include the change from baseline as the dependent variable, the fixed effect of treatments, and baseline CSF biomarkers measurement as covariate. The means, Least Squares (LS) means, a 2 sided 95% confidence intervals (CI) for each LS means, differences between LS means, a 2 sided 95% CIs for each difference and the p-values from model effects will be reported in the summary table.

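### The SAP's primary endpoint is an unnamed set of CSF biomarkers at two doses, each tested at 5%, with no lead, order, adjustment or rule for success

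*SAP*

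**What the plan says.** SAP 1.2.1 gives the primary endpoint as "the change in value of specific cerebral spinal fluid (CSF) biomarkers from the second screening to Day 28 between each dose group and placebo". It names no biomarker. Table 2 in SAP 6.1 uses the singular, "Change from Screening Visit 2 of the specific CSF biomarker on Day 28", and again names none. Protocol 10.4 lists nine CSF biomarker endpoints and labels none of them primary. SAP 2.1 lists ten CSF assays (it adds Aβ40) and leaves room for others.

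On testing, SAP 1.3 says: "The primary endpoint of CSF biomarker will be analyzed by ANCOVA at a significant level of 5% to test the null hypothesis". The hypotheses that follow are framed for one biomarker at a time and cover every pair of differing treatments. SAP 6.2.1 fits, for each biomarker, an ANCOVA of change on treatment and baseline. It reports least-squares means, their differences, "a 2 sided 95% CIs for each difference and the p-values from model effects will be reported in the summary table". SAP 4.4.1 adds, for all tests, that "a difference resulting in a p-value of less than or equal to 0.05 will be considered statistically significant".

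Neither document states a lead biomarker, an order of doses, a gatekeeping rule, a multiplicity adjustment, or a condition under which the primary endpoint counts as met.

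**The concern.** A 5% level has a clear meaning for one test. Here it attaches to each member of a family whose size is not stated, and any member that reaches 0.05 may be called a significant primary result. The error rate for the primary endpoint as a whole is therefore not 5%, and what counts as success is not fixed in advance.

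The family is probably not small. Protocol 10.4 lists nine CSF endpoints, and SAP 6.2.3 asks for the dose-response model to be repeated across the remaining CSF biomarkers, so all nine will probably be reported. With two doses, that makes 18 opportunities. The risk is selective emphasis: one biomarker at one dose crosses 0.05 and is presented as the primary finding. SAP section Introduction (Purpose) says the results may go into regulatory submissions and manuscripts.

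**Working it through.** **The plan's own figure.** The only error rate stated is 5% per test. In simulation, a single overall F test under no effect rejected 4.8% to 5.0% of the time, so the per-test level is reproduced. The documents state no family-wise rate to compare with.

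**Inputs from the documents**
- Three arms, 1:1:1, 60 patients, so 20 per arm (SAP 2.3.1, 2.7).
- Model: change on treatment plus own baseline (SAP 6.2.1). Error degrees of freedom = 60 − 3 − 1 = 56.
- Two-sided, significant at 0.05 or less (SAP 4.4.1).
- Number of CSF biomarkers: nine (protocol 10.4). That these nine are the primary set is an assumption.

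**Inputs assumed**
- Equal correlation ρ between biomarkers, 0 to 0.9. The documents give no value.
- Correlation of 0.7 between baseline and Day 28.
- Global null: no effect on any biomarker at either dose.

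**Number of tests**
- Each dose against placebo: 9 × 2 = 18.
- All pairs, adding 100 mg against 50 mg: 9 × 3 = 27.
- Overall F test: 9.

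**Closed-form check.** For nine independent F tests, 1 − 0.95⁹ = 0.370. For 18 independent tests, 1 − 0.95¹⁸ = 0.603. The true figure for 18 contrasts is a little lower even at ρ = 0, because the two contrasts for each biomarker share the placebo arm.

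**Simulation** (40,000 trials per cell; simulation standard error at most √(0.25/40,000) = 0.25 percentage points). Chance of at least one p-value of 0.05 or less, nine biomarkers:

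| What counts | ρ = 0 | 0.3 | 0.5 | 0.7 | 0.9 |
|---|---|---|---|---|---|
| 18 dose-versus-placebo contrasts | 57% | 52% | 44% | 34% | 22% |
| 27 pairwise contrasts | 69% | 63% | 54% | 42% | 27% |
| 9 overall F tests | 37% | 33% | 28% | 22% | 13% |

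The first row is the reading that SAP 1.2.1 best supports. The second takes the hypotheses of SAP 1.3 literally. The third takes the model-effect p-values of SAP 6.2.1 as decisive.

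**Smallest and larger families.** One biomarker at two doses gives about 9% by contrasts (1 − 0.95² = 9.75% if they were independent) and 5% by F test. Ten biomarkers, with Aβ40, give about 61% to 22% by contrasts and 40% to 13% by F test.

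**The case against.** **This is a small Phase 2b biomarker study.** The sample size has no stated power and the work is largely exploratory. That is fair, and it argues for a light remedy. But the SAP itself declares a primary endpoint, a null hypothesis, a 5% level and a significance rule, and those should mean what they say.

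**An isolated significant result could not be told from chance.** A reader might infer this, but it goes too far. SAP 6.2.1 reports every difference with its 95% interval, and SAP 4.4.1 shows p-values to four decimals. If all nine biomarkers are reported, a reader can apply a Bonferroni threshold of 0.05/18 = 0.0028: a p-value of 0.001 would survive it and 0.04 would not. A consistent pattern across biomarkers, which suits the replication objective, also stays readable. What remains is that the plan's own rule would label the 0.04 a significant primary result.

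**The plan has no deciding test at all.** This is also too strong. SAP 1.2.1 points to each dose against placebo. SAP 1.3 and 6.2.1 blur this, but the contrasts are the natural reading.

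**The F test protects.** No such gate is stated. If contrasts counted only after a significant F test for the same biomarker, the chance for nine biomarkers would still be about 32% to 11%, because the gate works within a biomarker and not across them.

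**Cognition is also primary.** As extracted, Table 2 shows "The Cambridge Cognition tests results" under the primary heading. SAP 1.2.2 lists among the secondary endpoints to "evaluate the change in Cambridge Cognition testing from the Day 1 to Day 28 between each dose group and placebo", and SAP 6.2.2 agrees. The table layout may be an artefact of reading the PDF, so it is not counted as a defect.

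**The biomarkers may be listed elsewhere.** SAP 8.0 refers to mock tables in a separate document, not seen here, which may name them. SAP 8.0 describes those shells as showing general layout, so they would not be expected to set a lead, an order or an error rate.

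**Conclusion.** The point stands. The SAP sets a 5% level for each test in a primary family that it does not name, with no lead, order, adjustment or success rule. On the reading SAP 1.2.1 best supports, and if the nine biomarkers of protocol 10.4 are meant, the chance of at least one false significant primary result is about 57% to 22%. Even at a correlation of 0.9 that is more than four times 5%.

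The omission is certain on the documents seen; the percentages are conditional. They rest on nine biomarkers, 20 per arm, a global null and an assumed correlation, which alone moves the main figure from 57% to 22%. They should not be quoted as the trial's actual error rate. Nor do the documents show an intention to choose biomarkers after the results are known: the SAP is to be final before unblinding. The defect is only that what counts as success is left open.

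**What to change.** Before unblinding, in SAP 1.2.1, 1.3, 4.4.1, 6.1 and 6.2.1:

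1. List the primary CSF biomarkers by name.
2. Name one lead biomarker and one lead dose-versus-placebo contrast, both the sponsor's choice, tested at two-sided 0.05 as the sole deciding test for the primary endpoint.
3. Take 100 mg against 50 mg out of the primary family.
4. Label all other biomarker p-values nominal, and limit the significance statement in SAP 4.4.1 accordingly. Keep all estimates and 95% intervals.

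This is wording only; data and visits do not change. The lead test keeps its full 5% level. The cost is that no formal claim can be made for the other dose or for the non-lead biomarkers.

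If the sponsor wants formal claims there, the alternative is Holm over all dose-versus-placebo tests. With nine biomarkers its first step is 0.05/18 = 0.0028. The detectable difference at 80% power is about (critical t + 0.848) × √(2/20), in residual SDs of the change, with 57 degrees of freedom (no covariate):
- at 0.05: (2.002 + 0.848) × 0.316 = 0.90 SD
- at 0.0028: (3.127 + 0.848) × 0.316 = 1.26 SD

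With 56 degrees of freedom, as in the SAP's ANCOVA, both values are the same to two decimals.

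As a minor check, confirm that Table 2 shows the Cambridge Cognition tests as secondary.

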2.0 Background

2.1 Study Design

This Phase 2b study is a randomized, double-blind, placebo-controlled trial of PTI-125 oral tablets given to patients with mild to moderate Alzheimer's Disease. Sixty patients are expected to be enrolled in the trial and randomized to one of the three cohorts. Cohorts will receive placebo or PTI-125 at 50 or 100 mg twice a day.

Two screening visits will be scheduled within 30 days of start of the study (Figure 1) Subjects meeting the initial screening criteria will return for a cerebrospinal fluid (CSF) draw at a second screening visit. A second CSF sample will be collected at day 28 visit for CSF biomarkers as well as analysis of PTI-125. Cambridge Cognition testing will be conducted at the second Screening visit, Day 1 and at the Day 28 visit.

On Screening visit 1 and Day 28, patients will be assessed for suicidality via the C-SSRS.

Subjects will report to the clinic on the morning of Day 1 and the following will be conducted: Cambridge Cognition testing, a full physical exam, an ECG and a blood draw for clinical labs and biomarkers. Subjects will be monitored for Adverse Events (AE) and Vital Signs (VS) will be taken through 2 hours post- dosing. Subjects will return to the clinic on Days 7, 14 and 28 for blood draws for clinical laboratory testing, safety assessments of vital signs, ECGs.

PK blood samples will be obtained prior to the first dose on Day 7, Day 14, and Day 28 for C_{min} values. On Day 28, there will be a CSF draw after the last dose, and an additional PK blood sample will be obtained after this CSF draw for calculation of CSF/plasma ratio.

Blood samples for testing in PTI-125Dx, the companion diagnostic/biomarker, mTOR activation and other potential blood-based biomarkers will be drawn on Day 1 and Day 28. The Day 14 blood sample will also be used for APOE genotyping. A CSF sample collection will be performed on Day 28 for neurogranin, neurofilament light chain, total tau, pTau (T181), A β 42, A β 40, YKL40, IL-6, IL-1 β , TNF α and other potential CSF biomarker assays as well as bioanalysis of PTI-125.

Figure 1. Study Design Schema

2.2 Inclusion/Exclusion Criteria

The inclusion and exclusion criteria are defined in the final protocol (Section 5.2) and apply to all subjects who consent to the study.

2.3 Treatment Groups

2.3.1. Randomization and Blinding

On Day 1, prior to dosing, 60 Subjects will be randomized at a 1:1:1 ratio to the following 3 treatment arms:

- 1. PTI-125: 50mg twice daily
- 2. PTI-125: 100 mg, twice a day
- 3. Matching Placebo, twice daily

Randomization will be performed using an Interactive Web Response System (IWRS).

Randomized treatments will be assigned by subject numbers in a randomly generated numeric sequence only after the subject has met all the I/E criteria.

As this is a double-blind, placebo-controlled study, the randomization code shall be blind to study subjects, investigators, clinical staff or study monitors until all subjects have completed therapy and the database has been finalized and locked.

2.3.2 Treatment Compliance

The investigator will be responsible for monitoring the receipt, storage, dispensing and accounting of all study medications. A summary of the total amount of medication taken by patient as per total daily dose and number of tablets per day should be provided by treatment groups.

2.4 Study Population

Approximately 60 subjects (male and female) with mild-to-moderate AD will be enrolled in the study. Dropouts may be replaced at the discretion of the Sponsor.

2.5 Study Drug and Dosing

PTI-125 tablets and placebo tablets are packaged in identical bottles affixed with a blinded label that includes the protocol number and treatment assignment number on the respective bottle. Placebo or PTI-125 will be supplied by Cassava Sciences (CSI) as coated tablets in 20-count bottles.

Study drug will be administered at least 1 hour before or after a meal twice a day. A dose can be up to 4 hours late, but if a dose is missed, the next dose should not be doubled.

2.6 Sample Size

Approximately 60 subjects will be enrolled in this study. Sample size was determined by estimating the intrasubject variability for log-transformed data from previous studies of new chemical entities. (in reference to Protocol section 10.6)

2.7 Schedule of Time and Events

Approximately sixty (60) subjects will be enrolled into the study and randomized to one of three cohorts [(Placebo or PTI-125 at 50 or 100 mg b.i.d. (n=20 per group)].

There will be two screening visits within 30 days of start of the study. Subjects that meet the randomization criteria will return to the clinic for subsequent visits at Days 1, 7, 14 and 28.

The schedule for assessments and timing of events is presented in Table 1

PROCEDURE	SCREEN 1 (Days -29 to Day -1)	SCREEN 2 (Days -28 to Day 0)	DAY 1 Time=0	DAY 7	DAY 14	DAY 28
Informed consent	Х	2				
Medical and medication histories	Х		x			
ECG	X		X		Х	Х
Vital signs	X		Х	Х	Х	Х
Physical examination	Х		*	*	*	X
FSH Test**	Х					
Biochemistry, hematology, urinalysis	Х		Х	х	Х	Х
MMSE	Х					X
HCV, HBsAg & HIV screen	Х					
Urine drug screen	Х					
Drug administration			Х	Х	Х	Х
Blood sample collection for PK analysis				х	X	х
Adverse Events		[X	Х	Х	Х
Blood draw for biomarkers and one time only, APOE genotyping			х			х
Cambridge Cognition testing		Х	Х		1	Х
C-SSRS	Х					Х
CSF draw		Х				Х

Table 1. Schedule of Time and Events

* Listen to heart and lungs ** If female and last natural menses < 24 months or uncertain

Page 12 of 22

3.0 Populations of Analysis Sets

All subjects who receive study medication will be included in analyses for safety.

All subjects for which data is available for both Screening 2 and Day 28, will be included in the biomarker analysis All subjects for which data is available for Day 1 and Day 28 will be included in the cognition analysis.

4.0 Data Analysis Considerations

4.1. Analysis Populations

There will be two analysis populations defined for this study.

4.1.1. Full Analysis Set Population (FAS)

The Full Analysis Set population includes all subjects who receive at least one dose of study treatment and have evaluable efficacy records at baseline and post-baseline visits. The Full Analysis Set population will be used for all efficacy analyses. Subjects will be analyzed as treated.

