4.1.2. Safety population (SP)

The Safety population will include all subjects who receive at least one dose of the study treatment. All safety analyses will be based on the Safety population. Subjects will be analyzed as treated.

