6.0 Efficacy Analysis

All the efficacy analyses will be performed using the FAS population.

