6.2.2 Secondary Efficacy Analysis

CSF Biomarkers at Screening Visit 2 and Day 28 will be compared by using the two tailed paired t-test per each treatment group (Placebo, PTI-125 50 mg, and PTI-125 100 mg). The analysis will be performed based on the FAS population. The means, differences between means of Screening Visit 2 and Day 28, a 2 sided 95% CIs for the difference and the p-values from the t-test will be reported in the summary table.

Cambridge Cognition Test

Results will be summarized for subjects by treatment group. The summary and statistical analysis will be conducted using FAS population. The change from baseline on Day 28 will be analyzed by using a General Linear Model for the ANCOVA. The model will include the change from baseline as the dependent variable, the fixed effect of treatments, and baseline Cambridge cognition measurement as covariate. The means, Least Squares (LS) means, a 2 sided 95% confidence intervals (CI) for each LS means, differences between LS means, a 2 sided 95% CIs for each difference and the p-values from model effects will be reported in the summary table.

Dose Response Analysis 6.2.3

Nonlinear Emax model will be used in dose-response analysis. The model has the following form:

$$R_i = E_0 + \frac{D_i^N \times E_{max}}{D_i^N + ED_{50}^N} + \varepsilon_i$$

Where:

i = patient;

 R_i = The value of response for patient i (ex. Defined to be "Change form Baseline in A β_{42} at Day 28" should be repeated for the remaining CSF Biomarkers);

 D_i = Concentration of the drug in the plasma of the patient *i* at Day 28;

 E_0 = Basal response, when the concentration of the drug is zero or minimal;

 E_{max} = The maximum response attributable to the drug;

ED₅₀ = The concentration that produces half of maximum response;

N = The slope measures the change in response by moving from one concentration level to another;

 ε_i = The random error term for patient *i* – i.i.d and follows normal distribution with mean – 0 and variance.

Treatment group response will be predicted by applying the Emax model which intrinsically has 4 parameters to estimate (E0, Emax, ED50, N). This can be performed with "Proc NLIN" procedure in SAS by arbitrary specifying starting estimates for these parameters by treatment groups.

To assure optimal convergence of the procedure, the following starting estimates will be applied:

	Placebo	PTI-125 50mg	PTI-125 100mg
E ₀	0	Minimum response from observed data	Minimum response from observed data

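### Every efficacy analysis, including the primary CSF ANCOVA, groups patients as treated, and no as-randomised efficacy analysis is planned (low severity)

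*SAP*

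**What the plan says.** SAP 4.1 limits the analysis sets: "There will be two analysis populations defined for this study". The first is the FAS, made up of dosed patients with usable efficacy data before and after treatment starts. SAP 4.1.1 sets its use and grouping: "The Full Analysis Set population will be used for all efficacy analyses. Subjects will be analyzed as treated". The second is the Safety population, for which SAP 4.1.2 says: "All safety analyses will be based on the Safety population. Subjects will be analyzed as treated".

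The FAS rule carries through to each between-group and within-group efficacy analysis:

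- SAP 6.0, general rule: "All the efficacy analyses will be performed using the FAS population".
- SAP 6.2.1, primary CSF biomarkers: "The baseline, post baseline, and change from baseline values will be summarized by treatment group based on the FAS population". The ANCOVA follows directly.
- SAP 6.2.2, paired t-tests within each group: "The analysis will be performed based on the FAS population".
- SAP 6.2.2, Cambridge Cognition: "The summary and statistical analysis will be conducted using FAS population".

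The Emax model in SAP 6.2.3 is little affected, because its dose term is not the arm but the "Concentration of the drug in the plasma of the patient" at Day 28. SAP 5.1 makes the same choice for disposition: completers and discontinuations at each site are counted by actual treatment, while percentages use the number randomised. Protocol 10.2 includes all dosed patients and states no grouping rule, so the as-treated rule comes from the SAP alone.

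**The concern.** Randomisation protects a between-arm comparison when patients are analysed in the arm to which they were assigned. As-treated grouping is a usual choice for safety. For efficacy it replaces the randomised groups with groups defined by what happened afterwards. An accidental mix-up under blinding does not by itself bias the as-treated estimate, but that grouping relies on the mix-up being unrelated to outcome. As-randomised grouping needs no such assumption.

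A mix-up could come to light, because Protocol 7.3.3 has one plasma sample from each placebo patient assayed for drug. If drug were found and the patient were judged to have taken active product, the as-treated rule would move that patient. With 20 per arm, one patient is 5% of a group, so a single move can shift the primary estimate.

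**Working it through.** **Inputs from the documents.** 60 patients randomised 1:1:1 (SAP 2.3.1), 20 per arm (Protocol 4, SAP 2.7), two-sided 5% tests (SAP 4.4.1). The sample-size sections (Protocol 10.6, SAP 2.6) give no effect size, SD or power, so there is no planned figure to reproduce. For scale, 20 per arm gives 80% power for √(2/20) × (1.960 + 0.842) = 0.886 SD (normal approximation).

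**Assumed.** Outcome SD = 1, the effects named below, and one full-course mix-up. The SE of a two-arm difference is √(2/20) = 0.316 SD.

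**Step 1: equal arm means, one patient moved.** A patient lying z from the common mean leaves one arm (19 remain) and joins the other (now 21). The shift is z/19 + z/21.

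- z = 0.8: 0.0421 + 0.0381 = 0.080 SD, or 0.25 SE.
- z = 2: 0.1053 + 0.0952 = 0.200 SD, or 0.63 SE.

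**Step 2: true effect E = 0.5 SD, one placebo-assigned patient on active drug.** That patient's value is E + z; all others sit at their arm means.

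- As randomised: E − (E + z)/20.
- As treated: E + z/21.
- Gap (as treated minus as randomised): z/21 + (E + z)/20.

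| z | Gap (SD) | Gap (SE) |
|---|---|---|
| 0 | +0.025 | +0.08 |
| +0.8 | +0.103 | +0.33 |
| −0.8 | −0.053 | −0.17 |
| +2 | +0.220 | +0.70 |
| −2 | −0.170 | −0.54 |

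**Step 3: expected as-randomised contrasts after one mix-up, with assumed effects of 0.4 SD (50 mg) and 0.8 SD (100 mg).** The affected arm's mean moves by 1/20 of the difference between the two products.

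| Assigned → received | 50 mg v placebo | 100 mg v placebo |
|---|---|---|
| No mix-up | 0.40 | 0.80 |
| Placebo → 100 mg | 0.36 | 0.76 |
| Placebo → 50 mg | 0.38 | 0.78 |
| 50 mg → placebo | 0.38 | 0.80 |
| 100 mg → placebo | 0.40 | 0.76 |
| 50 mg → 100 mg | 0.42 | 0.80 |
| 100 mg → 50 mg | 0.40 | 0.78 |

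For example, with a placebo patient given 100 mg the placebo mean becomes 0.8/20 = 0.04, so the contrasts are 0.80 − 0.04 = 0.76 (−5%) and 0.40 − 0.04 = 0.36 (−10%). Direction after a mix-up between doses depends on the dose effects: with the two effects swapped, 50 mg → 100 mg takes 50 mg v placebo from 0.80 to 0.78.

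**Step 4: simulated three-arm ANCOVA.** 3 × 20 patients, baseline slope 0.5, residual SD 1, effects as in step 3, one random placebo patient given 100 mg, 10,000 runs. The mean 100 mg v placebo estimate is 0.802 as treated and 0.761 as randomised, against a true 0.80. The mean absolute gap between the two is 0.27 SE and the 95th percentile 0.65 SE. A separate run gave 0.804, 0.766, 0.27 SE and 0.64 SE.

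**Step 5: type I error.** Two arms of 20, no true effect, t test without covariate, 40,000 simulated trials:

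| Placebo patients moved to active | One moved | Two moved |
|---|---|---|
| At random | 5.2% | 5.1% |
| From the most favourable quarter | 6.0% | 10.5% |
| The most favourable | 8.3% | 16.8% |

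With no move the rate is 5.1%. Random moves leave the error rate alone; only outcome-related moves raise it, and the last row is an upper bound.

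**The case against.** The strongest reply is that the SAP rule does better in the scenario most likely to arise. After a random mix-up, the as-treated estimate is close to the truth (0.802 against 0.80) and the as-randomised one is diluted (0.761). At a true difference of 0.886 SD, one placebo patient on active drug leaves power at 79.9% as treated but 75.9% as randomised. Nothing in the documents suggests an outcome-related mix-up, and the randomisation code stays concealed until database lock. This stands, and it keeps the severity low. It does not remove the reason for a primary analysis that needs no assumption about why a mix-up occurred.

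Three further points stand in part:

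- The SAP never defines as treated. That the groupings differ only when the wrong product is received is the ordinary reading of the term, and no rule covers mixed or partial exposure. Nor does any section say that the placebo plasma assay decides actual treatment. Grouping by randomised arm removes the question for the primary analysis, but not for safety or a sensitivity analysis.
- The change does not produce an all-randomised comparison. The FAS needs data before and after treatment starts, SAP 3.0 restricts the biomarker analysis to patients with both CSF samples, and SAP 4.3.4 rules out imputation. That is a separate limitation.
- The SAP 5.1 item is descriptive and minor. It matters only after a mix-up: with denominators by randomised arm and full completion, one regrouped patient would give 21/20 (105%) in one arm and 19/20 (95%) in another.

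A higher severity rating would rest on the outcome-related rows of step 5, for which the documents give no support.

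**Conclusion.** The concern holds, at low severity. The as-treated rule reaches the primary CSF ANCOVA, the paired t-tests and the cognition ANCOVA, and no as-randomised efficacy analysis exists in either document. The effect is zero if every patient receives the assigned product. If one patient does not, the primary estimate typically differs between the two groupings by about a quarter of a standard error, and by about two thirds at the 95th percentile of the simulation. These sizes depend on assumed SDs, effects and a full-course mix-up. They describe movement of the estimate, not demonstrated bias.

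**What to change.** In SAP 4.1.1, replace the last sentence of the FAS definition with: *Subjects will be analyzed according to the treatment to which they were randomized.* Keep as-treated grouping for the Safety population and, if wanted, for one labelled sensitivity analysis of the primary endpoint; say in one line how treatment received is determined for those uses. In SAP 5.1, count completion and discontinuation by randomised arm so that numerators match the stated denominator. Make the change before unblinding, when SAP finalisation is due.

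The cost is small: these short SAP edits, and use of the randomised-arm variable in the efficacy and disposition programs. Sample size and alpha are unchanged. The downside is the dilution or shift shown in step 3 if a mix-up occurs; the labelled sensitivity analysis would show its size.
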